## 9. Management of adverse events

### 9.1. Definition

#### **Adverse Event (AE)**

An adverse event (AE) is defined as any unfavorable and unintended sign, symptom or disease, regardless of whether it is considered related to the medical device or procedure that occurs during the course of the study.

In all cases, etiology will have to be researched and identified as soon as possible.

#### **Serious Adverse Event (SAE)**

A serious adverse event (SAE) is defined as any untoward medical occurrence that results in death, is life threatening, requires inpatient hospitalization or prolongation of existing hospitalization, results in persistent or significant disability/incapacity, or is a congenital anomaly/birth defect.

The investigator is responsible of transmission of SAE to the sponsor and the sponsor is responsible of transmission of the SAE declaration to the authorities.

### 9.2. Gradation

Adverse events should be categorized by the investigator according to severity:

- **Mild:** perception of sign or symptom, but **easily tolerated**.
- **Moderate:** **cumbersome** enough to impact subject activities.
- **Severe:** modifying **considerably** patient activities, or **impairing**, or constituting a **threat for the life** of the patient.

### 9.3. Causality

Main factors to take into account to determine the causality are:

- Events chronology,
- AE evolution when the product is not used anymore or used again,
- Existence of another etiology that could explain the AE,
- Existence of similar published or known AE.

## 9.4. Expected AE

The expected AEs of the Cefaly® Abortive Program device are:

- Reversible skin irritation at the place of electrode
- Allergic reaction to the gel of the electrode (1 out of 1000)
- Pain during the session
- Sleepiness
- Neck pain
- Nausea
- Tooth pain

Paraesthesia, tingling/itching and burning sensation are normal effects of the device and should therefore NOT be considered as AEs, unless this sensation leads to treatment discontinuation.

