#### 3.2. Safety outcomes

Device safety will be assessed by the number of reported adverse events (AE) and their severity.

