#### 4.2.4. Final visit

The patient will be instructed to return to the investigation site within approximately 4 days after the treatment session to return the study material, i.e. the Cefaly® Abortive Program device as well as completed paper diary and AE reporting form. The investigator will review the diary in details to ensure data completeness and accuracy (to avoid any missing data, unclear data or discrepancies). If necessary, the investigator will instruct the patient to make him/herself corrections and to sign the corrections with his/her identification (screening) number and the date (no initials).

All adverse events reported on the AE reporting form will be reviewed by the investigator to assess severity. The investigator will also ask the patient if he/she has experienced any adverse effects not reported on the form. Additionally, the investigator will ask the patient if he/she has experienced any device defects.

If a patient has not treated a migraine attack within two months following the screening visit, the study material (Cefaly® Abortive Program device with accessories) will have to be returned to the study site. This will be considered as a protocol violation.

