#### 6.1.2. Sham device

The Cefaly® Abortive Program sham device will be programed with the following parameters: rectangular biphasic pulse current, with similar pulse width (250  $\mu$ s), at a linearly increasing intensity sufficient for the patient to feel strong paraesthesia similar to that produced by the verum device, but with a different frequency that will not induce a sedative effect to the central nervous system (1).

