## 8. Data management and statistics

### 8.1. Data management

Each patient who signs a consent form to participate in the study will be assigned a unique identification number (i.e. patient screening number) for identification purposes. Each patient should be assigned only one number. Should the patient fail to qualify for the study, his/her identification (screening) number must not be re-used for any other patient in the study.

CRF and paper documents provided to the patient (i.e. diary and AE reporting form) will include the unique patient identification (screening) number in the header.

The collected data will be included in the following source documents: patient's case report form (CRF) and diary. These completed documents will be provided by the investigator to the sponsor. In practice, the investigator records these completed documents in an appropriate binder and sends the scan of the documents by email to the sponsor. Tracking of completed source documents is performed: when a patient completed the clinical investigation but the related source documents have not been received, an email is sent to the investigator/study coordinator to request missing documents.

Duration, intensity and/or interruption of the treatment are recorded for each patient thanks to a built-in electronic system in the device. Each device will bear a unique randomization number that has to be reported in the patient's CRF and will allow to identify which device was used by each patient.

In case of lack of data accuracy (missing data, unclear data, discrepancies), a Data Clarification Form is sent to the investigator. The completed and signed form is sent back to the sponsor. Tracking of Data Clarification forms is performed to ensure that all Data Clarification forms are completed by the investigator/study coordinator.

AE and SAE are collected and investigators will report SAE and AE to the sponsor using the specific collecting forms annexed to the CRF. These SAE and AE collecting forms will be reviewed and analysed by the sponsor when received. The device defects are also collected and investigators will report device defects to the sponsor using the CRF.

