### 8.2.4. Statistical analysis

#### Efficacy analysis

The efficacy analysis will be executed on a modified intention-to-treat (mITT) basis.

Patient data will be included in the mITT analysis if all the four following conditions are met:

1. The patient treated a qualifying migraine.
2. The patient applied the Cefaly® Abortive Program treatment (verum or sham) during at least 30 minutes\*.
3. The headache pain severity score **AND** the migraine-associated symptom(s) at baseline were reported in the diary.
4. The headache pain severity score **OR** the migraine-associated symptom(s) at 2 hours were reported in the diary.

\*If the patient stopped the 2-hour treatment session after 30 minutes but before its end for any reason, he/she is kept in the modified intention-to-treat (mITT) analysis if all the other conditions are met.

If the patient takes anti-migraine rescue medication between 2 hours and 24 hours after the beginning of the e-TNS treatment session, the headache pain intensity and migraine-associated symptoms presence

can be affected by the medication and the last value carried forward method (2-hour value carried forward method in this case) will be applied for the 24-hour time point headache pain severity and migraine-associated symptoms.

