#### Safety analysis

A safety analysis will be performed in case of reported adverse events comparing both groups (verum versus sham). The safety analysis will be performed on all randomized patients, i.e. patients who underwent at least the e-TNS training test session.

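### Section 9.4 ties the AE status of itching and burning to stopping treatment, not to severity, so non-serious moderate or severe cases borne to the end can go uncounted and ungraded

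*Combined protocol and SAP*

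**What the plan says.** Section 9.4 lists the expected AEs and then sets one group of sensations aside: paraesthesia, tingling or itching and "burning sensation are normal effects of the device and should therefore NOT be considered as AEs, unless this sensation leads to treatment discontinuation". The same list names session pain and reversible skin irritation as AEs, with no stopping condition attached to either.

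Four other sections depend on AE status:

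- **3.2 Safety outcomes:** "Device safety will be assessed by the number of reported adverse events (AE) and their severity".
- **9.2 Gradation:** AEs are graded by their effect on the patient. Moderate, for instance, means burdensome "enough to impact subject activities". Neither the moderate nor the severe grade requires that treatment be stopped.
- **9.5 AE collection:** AEs go onto the forms annexed to the CRF.
- **8.2.4 Safety analysis:** the arms are compared on reported AEs, in randomised patients who had at least the training session.

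A sensation might also surface elsewhere. The patient has an AE reporting form. At the final visit (4.2.4), "The investigator will also ask the patient if he/she has experienced any adverse effects not reported on the form". The device keeps a log, so that "Duration, intensity and/or interruption of the treatment are recorded for each patient" (8.1). The diary items (4.2.2, 4.2.3, 7.1) cover the attack itself, its symptoms and rescue medication; device sensations are not among them.

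**The concern.** For itching and burning, 9.4 replaces the severity scale with a single question: did the patient stop? Stopping is an imperfect stand-in for severity in this trial. Patients are asked to complete two hours, a stopped device may not be restarted, and rescue medication is barred during those two hours. A patient who wants the attack treated has reason to put up with discomfort.

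At stake is the description of tolerability. A reader of the safety result could not tell how often a two-hour session, at up to 16 mA in the verum arm (6.1.1), caused moderate or severe itching or burning that patients sat through. The comparison between arms cannot supply this. The sham intensity is set to be "sufficient for the patient to feel strong paraesthesia similar to that produced by the verum device", so a small difference between arms would not show that unpleasant sensation is rare or mild. The frequency within each arm is needed.

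**Working it through.** The plan gives no rate for these sensations, so there is no figure of its own to reproduce. The point rests on reading the sections together.

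**Step 1: which rule governs.** Section 9.1 defines an AE as something both unfavourable and unintended. Section 9.4 is more specific and, for the named sensations, overrides it. Its only exception is discontinuation.

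**Step 2: what follows.** Sections 9.2, 9.5, 3.2 and 8.2.4 apply to AEs. A sensation that 9.4 classes as not an AE has no stated route into the grading, the count or the arm comparison. No section provides for tabulating it separately.

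**Step 3: what is still captured.**

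- Cases that lead to stopping are AEs under 9.4.
- Cases meeting a seriousness criterion fall under the SAE definition in 9.1, which is stated independently of 9.4.
- Cases filed as session pain or skin irritation are AEs whether or not the patient stopped. No rule separates burning from pain, or itching from irritation, so this depends on the words used.
- The AE form and the final-visit question may bring out a report, but 9.4 then decides its status.

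**Step 4: the remaining gap.** What is left out is itching or burning that is moderate or severe, non-serious, filed as such and borne to the end.

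**Step 5: the training session.** Inability to bear the 20-minute session is exclusion criterion 14, and these patients belong to the safety population. Section 9.4 does not say whether such a failure counts as treatment discontinuation.

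**Step 6: illustration of size.** Inputs:

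- N = 300 per arm (at least 600 patients, 1:1; section 5).
- q = assumed share of an arm with moderate or severe non-serious itching or burning filed as such.
- s = assumed share of those patients who stop.

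Cases omitted = N × q × (1 − s).

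| q | cases, 300 × q | omitted, s = 10% | omitted, s = 50% | omitted, s = 100% |
|---|---|---|---|---|
| 2% | 6 | 6 × 0.9 = 5.4 | 6 × 0.5 = 3 | 0 |
| 5% | 15 | 15 × 0.9 = 13.5 | 15 × 0.5 = 7.5 | 0 |
| 10% | 30 | 30 × 0.9 = 27 | 30 × 0.5 = 15 | 0 |

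If every such case is filed as pain or irritation, q = 0 and nothing is lost. If the 20% loss in 8.2.1 leaves 300 × 0.8 = 240 per arm with a home session, the figures for that session shrink by a fifth (27 becomes 21.6). All values of q and s are assumptions.

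**Step 7: what a table by arm would show.** With 300 patients, 15 cases (5%) would have an exact (Clopper-Pearson) 95% interval of 2.8% to 8.1%, and 30 cases (10%) one of 6.8% to 14.0%. That is precise enough to describe tolerability.

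**The case against.** The case for leaving 9.4 alone has several sound parts.

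- **Intended effects.** Strong paraesthesia is built into both devices, so paraesthesia and tingling fit badly with an AE definition that requires the sign to be unintended. This stands, and the fix leaves those two alone. The argument is weaker for burning.
- **A narrow gap.** Session pain and skin irritation are AEs without conditions, and serious outcomes are reported regardless. This stands, and it limits the point to the gap in step 4.
- **Screening.** Patients who cannot bear the training session do not go on to home treatment, and the training device uses the same stimulation parameters and ramp times. The illustration makes no allowance for this. A 20-minute screen should shrink the pool, but it does not rule out discomfort later in two hours.
- **Little sign of trouble before.** Section 1 reports one AE, nausea, and no other complaints in the previous sham-controlled trial of a one-hour session. That is a shorter session, mostly given in the clinic, and the documents do not say whether a convention like 9.4 applied there.

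A reader might also infer that the stopping test cannot be applied because the reason for stopping goes unrecorded. Section 8.2.4 does retain patients without regard to cause: "If the patient stopped the 2-hour treatment session after 30 minutes but before its end for any reason". However, the CRF and its annexed forms are not among the documents, so the absence of a reason field cannot be inferred. A sensation that stops treatment is itself an AE, and 9.5 then calls for its nature, causality and countermeasures.

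**Conclusion.** The point holds in limited form. As written, 9.4 leaves out of the safety count and grading any non-serious moderate or severe itching or burning that is filed as such and borne to the end. This follows from the text and needs no assumption about rates. The size does need one: the documents give none, and the loss may be nil. Under the assumed 2% to 10% of an arm and 10% to 100% stopping, it ranges from 0 to 27 cases per arm.

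A reader might infer that the rule biases the verum-sham safety comparison, either hiding a difference or creating one. The documents do not support that. The rule is identical in both arms and the sham is designed to feel similar. Distortion would require particular stopping shares in each arm, about which nothing is known. Nor do the documents support the view that serious events are hidden or that efficacy is touched. This is a cheap improvement to the description of tolerability, not a threat to the trial's main conclusions.

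**What to change.** In 9.4:

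- Keep paraesthesia and tingling as expected sensations that are not AEs unless they lead to stopping. Separate itching from tingling, which the section now treats as one item.
- Have every patient asked about itching and burning after the training session and after the two-hour session, with the answers graded on the 9.2 scale whether or not the patient stopped.
- State that inability to bear the training session because of such a sensation counts as discontinuation.

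In 8.2.4, add a descriptive table of these sensations, N and %, by arm, grade and session, kept separate from other AEs and including patients who finished as well as those who stopped. No significance test is needed.

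The cost is one added question per session. Asking directly will raise the reported rates in both arms. Grades from the home session will be partly mixed with the effect of the migraine on activities, again in both arms; the training session takes place outside the treated attack and is less affected. Sample size, devices and efficacy analysis do not change.

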## 9.5. AE collection

The patients are instructed to report all AEs to the investigator. AEs will be analyzed by the investigator who will document it in the specific collecting forms annexed to the CRF.

All AEs will be collected in the specific collecting forms annexed to the CRF, specifying:

- Their nature
- Start date and duration
- Causality (according to investigator's opinion)
- Countermeasures and results

If the AE is a SAE, the sponsor should be notified as soon as possible.

## 9.6. Investigator's responsibility with respect to a SAE.

### 9.6.1. SAE Notification

Each SAE will be described on the specific form with as much detail as possible. The information to be communicated to the sponsor are:

- Patient identification (screening) number

- AE severity
- Start and end date
- Detailed description
- AE evolution
- Current diseases and relevant medical history of the patient
- Patient received treatments
- Causality link with the device under test

The investigator should also join to the AE report, each time it is possible:

- A copy of the hospitalization report
- A copy of all complementary exam results performed, including relevant negative results and joining the laboratory reference values
- Or any other document that he/she found useful and relevant
- Possibly, a copy of the autopsy report

All documents will be made anonymous and will bear the identification (screening) number of the subject.

#### 9.6.2. Modalities of notification to the sponsor

All SAE, no matter its causality relationship with the device under test, should be declared by the investigator:

- To sponsor (represented by the CEO)
- As fast as possible
- By e-mail: see the specific form annexed to the CRF

#### 9.6.3. Monitoring

The monitoring is ensured until total recovery, stabilization or death of the patient, on common decision of the monitor and the investigator. Related costs are covered by the sponsor.

#### 9.6.4. Notification period

It is the investigator responsibility to notify the sponsor about any SAE occurring:

- During the whole study period
- At any time, after the end of the study if the investigator thinks this could be related to the device under test during the study (if no other cause than the research could reasonably explain it).

## 9.7. Notification by the sponsor to the authorities

In case the sponsor is notified of an unexpected AE, he will report it directly to the national competent authority (FDA) and to the relevant Investigational Review Board(s).

Similarly, if a new fact relevant to the study or to the device appears that could impact the safety of the subjects participating to the study, the sponsor takes the appropriate emergency measures. The sponsor also notifies both the FDA and the IRB of this new fact and of the taken measures.

The delay to inform the authorities will be 2 days in case of death or life-threatening AE, and 15 days in case of other unexpected AE or new fact. An extra delay of 8 days is foreseen to provide a follow-up report.

If necessary, the investigator will ask the subjects participating to the study to confirm their consent based on the updated information.

NOTE: In case of findings that could affect adversely the safety of subjects or impact the conduct of the trial, the sponsor has to notify all concerned investigator(s).

